6.2. Secondary Endpoints

6.2.1. Confirmed OR by INV

The primary analysis performed on OR by ICR will be repeated on OR based on INV applying the same rules.

6.2.2. Confirmed IC-OR by ICR/INV

IC-OR by ICR

Analysis set: Participants with CNS metastases based on ICR

IC-OR by INV

Analysis set: Participants with CNS metastases based on Investigator Assessment

Analysis methodology:

The IC-OR, based on ICR/INV, will be summarized similar to OR (as described above in section 6.1 and 6.2), in Per Protocol Population Participants with CNS metastases based on ICR/INV. Surgery or radiotherapy of extracranial lesions will not affect the determination of IC-OR.

6.2.3. TTR by ICR/INV

Analysis set: Subsets of Participants with confirmed objective response by ICR/INV

Analysis methodology: TTR (months) = [first date of CR/PR which is subsequently confirmed-date of first dose+1]/30.4375

For participants whose OR proceeds from PR to CR, the onset of PR is taken as the onset of response.

Intercurrent events and missing data: data on response after subsequent anti-cancer therapy is administered will be excluded.

Summaries used for reporting: TTR will be summarized based on both ICR/INV assessment using simple descriptive statistics (mean, std, median, min, max, Q1, Q3, IQR).

6.2.4. IC-TTR by ICR/INV

Analysis set: Subsets of Participants with confirmed Intra-Cranial objective response by ICR/INV

Analysis methodology: IC-TTR (months) = [first date of CR/PR in brain lesions which is subsequently confirmed-date of first dose+1]/30.4375

For participants whose IC-OR proceeds from PR to CR, the onset of PR is taken as the onset of response.

DMB02-GSOP-RF02 4.0 Statistical Analysis Plan Template 01-Nov-2018 PFIZER CONFIDENTIAL Page 26 TMF Doc ID: 98.03 **Intercurrent events and missing data**: data on response after subsequent anti-cancer therapy is administered will be excluded.

Summaries used for reporting: IC-TTR will be summarized based on both ICR/INV assessment using simple descriptive statistics (mean, std, median, min, max, Q1, Q3, IQR).

6.2.5. DoR by ICR/INV

Analysis set: Subsets of Participants with confirmed objective response by ICR/INV

Analysis methodology:

DoR will be calculated on every participant showing OR as follows:

DoR (months) = [first date of PD or death/censoring - first date of CR/PR subsequently confirmed+1]/30.4375

Censoring for DOR will be identical to the censoring rules presented for PFS. Participants with an event more than 14 weeks after the last adequate tumor assessment will be censored on the date of the last adequate tumor assessment prior to the gap that documented no progression. If a new anti-cancer therapy starts prior to an event, the participant will be censored on the date of the last adequate tum or assessment that documented no progression prior to start of the new anti-cancer therapy.

Intercurrent events and missing data: data on response after subsequent anti-cancer therapy is administered will be excluded

Summaries used for reporting: Kaplan-Meier estimates (product-limit estimates) will be presented together with a summary of associated statistics including the median DR time with two-sided 95% CIs. The CIs for the median will be calculated according to Brookmeyer and Crowley.

When the number of participants with PD after a confirmed CR or PR is small, the use of Kaplan-Meier method is limited due to high number of censored observation, so the DOR will be summarized using number (%) of participants with events and of participants censored with DOR in the following categories: less than 6 months, $\geq 6 - <9$, $\geq 9 - <12$, $\geq 12 - <15$, $\geq 15 - <18$, $\geq 18 - <21$, $\geq 21 - <24$, and ≥ 24 months

6.2.6. IC-DoR by ICR/INV

Analysis set: Subsets of Participants with confirmed Intra-Cranial objective response by ICR/INV

Analysis methodology: IC-DoR (months) = [first date of PD in brain lesions or death/censoring – first date of IC OR (CR/PR subsequently confirmed)+1]/30.4375

For participants whose IC-OR proceeds from PR to CR, the onset of PR is taken as the onset of response.

DMB02-GSOP-RF02 4.0 Statistical Analysis Plan Template 01-Nov-2018 PFIZER CONFIDENTIAL Page 27 TMF Doc ID: 98.03 Censoring for DOR will be identical to the censoring rules presented for PFS.

Intercurrent events and missing data: data on response after subsequent anti-cancer therapy is administered will be excluded.

Summaries used for reporting: The IC-DoR, based on ICR/INV, will be summarized similar to DoR (as described above in section 6.2.5), in Per Protocol Population Participants with CNS metastases based on ICR/INV. Surgery or radiotherapy of extracranial lesions will not affect the determination of IC-OR.

6.2.7. PFS by ICR/INV

Analysis set: ITT: All enrolled participants who take at least 1 dose of Lorlatinib

Analysis methodology:

PFS is defined as the time from date of first dose to the date of the first documentation of PD per RECIST v1.1 as assessed by ICR/INV or death due to any cause, whichever occurs first and will be summarized in months:

PFS (months) = [date of event or censoring-date of treatment start +1]/30.4375.

PFS data will be censored as follows:

- For participants who start a new anti-cancer therapy prior to an event, censoring will be at the last adequate tumor assessment (see Section 5.2.9) prior to the start of new anti-cancer therapy. Note: if date of progression occurs on the same date as the start of new anti-cancer therapy, the progression will be counted as an event.
- For participants with documented progression or death after two or more missing tumor assessments, censoring will occur at the last adequate tumor assessment prior to the missing assessments. In this study antitumor activity will be assessed through radiological tumor assessments conducted at screening and every 6 weeks until disease progression regardless of initiation of subsequent anti-cancer therapy. The allowable time window for disease assessments is ±1week while on treatment and whenever disease progression is suspected (eg, symptomatic deterioration). Therefore time without adequate assessment is defined as 98 days (12 weeks plus 2 weeks).
- For participants who do not have an adequate baseline tumor assessment or who do not have any post-baseline tumor assessments, censoring will occur on the date of first dose unless death occurred on or before the time of the second planned tumor assessment (ie, on or before day 98) in which case the death will be considered an event. Note for participants who died without any post baseline assessments and meet the definition of two or more missing assessment the reason for censoring will be documented as two or more missed assessments and censoring will occur on the date of first dose.
- All other participants alive without objective progression will be censored on the date of the last adequate tumor assessment.

DMB02-GSOP-RF02 4.0 Statistical Analysis Plan Template 01-Nov-2018 PFIZER CONFIDENTIAL Page 28 TMF Doc ID: 98.03 The date of tumor response at each nominal timepoint based on the ICR/INV assessments will be used for determining the dates of last adequate assessment for censoring purposes.

The censoring and event date options to be considered for the PFS analysis are presented in Table 2.

Table 2.	Outcome and	event dates	for PFS	analyses
----------	-------------	-------------	---------	----------

Scenario	Date of event/censoring	Outcome
No adequate baseline assessment	date of first dose	Censored ^a
Progression or death \leq 98 days after last adequate tumor assessment or \leq 98 days after date of first dose	Date of progression or death	Event
Progression or death > 98 days after the last adequate tumor assessment ^b	Date of last adequate assessment ^b documenting no	Censored
No progression	PD prior to anti-cancer therapy or missed assessments	
New anti-cancer therapy given prior to PD	therapy of missed assessments	

^a if the participant dies \leq 98 days after date of first dose the death is an event on the death date

^b if there are no adequate post-baseline assessments prior to PD or death, then the time without adequate assessment should be measured from the date of first dose; if the criteria were met the censoring will be on the start date.

Summaries used for reporting:

Kaplan-Meier estimates (product-limit estimates) will be presented together with a summary of associated statistics including the median PFS time with two-sided 95% CIs. The PFS rate at 12 months will be estimated with corresponding two-sided 95% CIs. The CIs for the median will be calculated according to Brookmeyer and Crowley and the CIs for the survival function estimates at the timepoints defined above will be derived using the log(-log) method according to Kalbfleisch and Prentice (conftype=loglog default option in SAS Proc LIFETEST). The estimate of the standard error will be computed using Greenwood's formula.

Frequency (number and percentage) of participants with each event type (PD or death) and censoring reasons will be presented along with the overall event and censor rates. Reasons for censoring will be summarized according to the categories in Table 3. If a participant meets multiple definitions for censoring the list will be used to define the hierarchy.

Hierarchy	Condition	Censoring Reason
1	No adequate baseline assessment	No adequate baseline assessment
2	Start of new anti-cancer therapy before event.	Start of new anti-cancer therapy
3	Event more than 98 days from last adequate post-baseline tumor assessment/start date	Event after missing assessments ^a

 Table 3.
 Censoring Reasons and Hierarchy for PFS analyses

DMB02-GSOP-RF02 4.0 Statistical Analysis Plan Template 01-Nov-2018 PFIZER CONFIDENTIAL Page 29 TMF Doc ID: 98.03

4	No event and withdrawal of consent date ≥ start date OR End of study (EOS) = Subject refused further follow-up	Withdrawal of consent
5	No event and lost to follow-up in any disposition page	Lost to follow-up
6	No event and EOS page present and no adequate post-baseline tumor assessment	No adequate post-baseline tumor assessment
7	No event and none of the conditions in the prior hierarchy are met	Ongoing without an event

^a more than 98 days after last adequate tumor assessment.

The PFS time or censoring time and the reasons for censoring will also be presented in a participant listing.

6.2.8. TTP by ICR/INV

Analysis set: ITT: All enrolled participants who take at least 1 dose of Lorlatinib

Analysis methodology:

TTP is defined as the time from date of first dose to the date of the first documentation of PD per RECIST v1.1 as assessed by ICR/INV and will be summarized in months:

TTP (months) = [date of PD or censoring–date of treatment start +1]/30.4375.

TTP data will be censored as follows:

- For participants who start a new anti-cancer therapy prior to an event, censoring will be at the last adequate tumor assessment (see Section 5.2.9) prior to the start of new anti-cancer therapy. Note: if date of progression occurs on the same date as the start of new anti-cancer therapy, the progression will be counted as an event.
- For participants with documented progression or death after two or more missing tumor assessments, censoring will occur at the last adequate tumor assessment prior to the missing assessments. In this study antitumor activity will be assessed through radiological tumor assessments conducted at screening and every 6 weeks until disease progression regardless of initiation of subsequent anti-cancer therapy. The allowable time window for disease assessments is ±1week while on treatment and whenever disease progression is suspected (eg, symptomatic deterioration). Therefore time without adequate assessment is defined as 98 days (12 weeks plus 2 weeks).
- For participants who do not have an adequate baseline tumor assessment or who do not have any post-baseline tumor assessments, censoring will occur on the date of first dose unless death occurred on or before the time of the second planned tumor assessment (ie, on or before day 98) in which case the death will be considered an event. Note for participants who died without any post baseline assessments and meet the definition of

DMB02-GSOP-RF02 4.0 Statistical Analysis Plan Template 01-Nov-2018 PFIZER CONFIDENTIAL Page 30 TMF Doc ID: 98.03 two or more missing assessment the reason for censoring will be documented as two or more missed assessments and censoring will occur on the date of first dose.

• All other participants alive without objective progression will be censored on the date of the last adequate tumor assessment.

The date of tumor response at each nominal timepoint based on the ICR/INV assessments will be used for determining the dates of last adequate assessment for censoring purposes.

The censoring and event date options to be considered for the TTP analysis are presented in Table 4.

Scenario	Date of event/censoring	Outcome
No adequate baseline assessment	date of first dose	Censored
Progression \leq 98 days after last adequate tumor assessment or \leq 98 days after date of first dose	Date of progression	Event
Death \leq 98 days after last adequate tumor assessment or \leq 98 days after date of first dose	Date of death	Censored
Progression or death > 98 days after the last adequate tumor assessment ^a	Date of last adequate assessment ^b documenting no	Censored
No progression	PD prior to anti-cancer therapy or missed assessments	
New anti-cancer therapy given prior to PD	therapy of missed assessments	

 Table 4.
 Outcome and event dates for TTP analyses

^a if there are no adequate post-baseline assessments prior to PD or death, then the time without adequate assessment should be measured from the date of first dose; if the criteria were met the censoring will be on the start date.

Summaries used for reporting:

Kaplan-Meier estimates (product-limit estimates) will be presented together with a summary of associated statistics including the median TTP time with two-sided 95% CIs. The TTP rate at 12 months will be estimated with corresponding two-sided 95% CIs. The CIs for the median will be calculated according to Brookmeyer and Crowley and the CIs for the survival function estimates at the timepoints defined above will be derived using the log(-log) method according to Kalbfleisch and Prentice (conftype=loglog default option in SAS Proc LIFETEST). The estimate of the standard error will be computed using Greenwood's formula.

Frequency (number and percentage) of participants with PD and each censoring reasons will be presented along with the overall event and censor rates.

Reasons for censoring will be summarized according to the categories in Table 5. If a participant meets multiple definitions for censoring the list will be used to define the hierarchy.

Hierarchy	Condition	Censoring Reason
1	No adequate baseline assessment	No adequate baseline assessment
2	Start of new anti-cancer therapy before event.	Start of new anti-cancer therapy
3	Event more than 98 days from last adequate post-baseline tumor assessment/start date	Event after missing assessments ^a
4	No event and withdrawal of consent date ≥ start date OR End of study (EOS) = Subject refused further follow-up	Withdrawal of consent
5	No event and lost to follow-up in any disposition page	Lost to follow-up
6	No event and EOS page present and no adequate post-baseline tumor assessment	No adequate post-baseline tumor assessment
7	No event and Death recorded in any disposition page or Notice of Death	Patient died
8	No event and none of the conditions in the prior hierarchy are met	Ongoing without an event

Table 5.	Censoring Reasons an	d Hierarchy for T	TP analysis
----------	-----------------------------	-------------------	-------------

^a more than 98 days after last adequate tumor assessment.

The TTP time or censoring time and the reasons for censoring will also be presented in a participant listing.

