	• Using the Kaplan-Meier method, estimate its associated statistics on TTP (including the median TTP with two-sided 95% CI, the TTP rates at clinically meaningful timepoints with two-sided 95% CI) for all participants who received at least one dose of lorlatinib without regard to discontinuation from treatment unless death occurs, new anti-cancer therapy is initiated or extended gap in tumor assessment is present prior to progression. TTP is defined as the time from date of first dose to the date of the first documented PD.				
	This analysis is based on ITT population. Participants with an event more than 12 weeks (24 weeks post the first 42 weeks) after the last adequate tumor assessment will be censored on the date of the last adequate tumor assessment prior to the gap that documented no progression. If the participant dies before progression, the participant will be censored on the date of death. If a new anticancer therapy starts prior to an event, the participant will be censored on the date of the last adequate tumor assessment that				

Endpoint	Statistical Analysis Methods				
	documented no progression prior to start of the new anti-cancer therapy. Participants with inadequate baseline assessment or with a adequate post-baseline tumor assessments within 12 weeks after the start date will be censored on the start date, unless the participant dies within 12 weeks of the start date, in which case, the patient who be censored on date of death. The CI for the median TTP will be calculated according to Brookmeyer and Crowley method, and the CIs for the survival function estimates at the timepoints will be derived using the log(-log) method.				
	PFS by ICR/INV				
	• Using the Kaplan-Meier method, estimate its associated statistics of PFS (including the median PFS with two-sided 95% CI, the PFS rates at clinically meaningful timepoints with two-sided 95% CI) for all participants who received at least one dose of lorlatinib without regard to discontinuation from treatment unless new anti-cancer therapy is initiated or an extended gap in tumor assessment is present prior to progression or death. PFS is defined as the time from date of first dose to the date of the first documented PD or death due to any cause, whichever occurs first.				

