	This analysis is based on ITT population. Participants with an event more than 12 weeks (24 weeks post the first 42 weeks) after the last adequate tumor assessment will be censored on the date of the last adequate tumor assessment prior to the gap that documented no progression. If a new anti-cancer therapy starts prior to an event, the participant will be censored on the date of the last adequate tumor assessment that documented no progression prior to start of the new anti-cancer therapy. Participants with inadequate baseline assessment or with no adequate post-baseline tumor assessments within 12 weeks after the start date will be censored on the start date, unless the participant dies within 12 weeks of the start date, in which case, death will be an event on date of death. The CI for the				
	median PFS will be calculated according to Brookmeyer and Crowley method, and the CIs for the survival function estimates at the timepoints will be derived using the log(-log) method.				

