 To assess secondary measures of clinical efficacy 	 The estimand for Objective Response (OR) by investigator (INV) follows the estimand specified for the primary endpoint except that the treatment effect is based on INV The estimand for Intracranial (IC) response is the Intracranial treatment effect (ie in brain lesions) of lorlatinib from time of first dose until Intracranial progression is met or subsequent anti-cancer therapy is administered for all participants who receive at least one dose of lorlatinib without regard to discontinuation from treatment; all response assessments regardless of gaps in tumor assessments are considered The estimand for Time to Tumor Response (TTR) is the treatment effect from the time of first dose to the first date of response that is subsequently confirmed for all participant who are responders to lorlatinib 	 Every endpoint assessed by RECIST version 1.1 Confirmed Objective Tumor Response assessed per INV Confirmed Intracranial tumor response assessed per ICR/INV TTR per ICR/INV DOR per ICR/INV Duration of Intracranial response (IC-DOR) per ICR/INV PFS per ICR/INV TTP per ICR/INV

 The estimand for Duration of Response (DOR) is the treatment effect from the first date of OR that is subsequently confirmed for all participant who are responders to lorlatinib until progression or death, without regard to discontinuation from treatment unless new anti-cancer therapy is initiated or extended gap in tumor assessment is present prior to progression or death The estimand for IC-DOR follows the estimand specified for the DOR, but limited to intracranial lesions 	
 The estimand for Progression Free Survival (PFS) is the treatment effect from the time of first dose for all participants who receive at least one dose of lorlatinib until progression or death, without regard to discontinuation from treatment unless new anti- cancer therapy is initiated or an extended gap in tumor assessment is present prior to progression or death 	
• The estimand for Time to Tumor Progression (TTP) is the treatment effect from the time of first dose	

DMB02-GSOP-RF02 4.0 Statistical Analysis Plan Template 01-Nov-2018 PFIZER CONFIDENTIAL Page 7 TMF Doc ID: 98.03

	for all participants who receive at least one dose of lorlatinib until progression, without regard to discontinuation from treatment unless participant dies, new anti- cancer therapy is initiated or extended gap in tumor assessment is present prior to progression	

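### SAP 6.2.8 counts some early deaths as TTP events, while its own Table 4 and Table 5 and protocol 9.4.1 censor them

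*SAP*

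**What the plan says.** SAP 3.2.8 and 6.2.8 define TTP from first dose to first documented PD. The formula in 6.2.8 ends at PD or censoring and has no term for death.

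Four censoring bullets follow. The third applies when there is no adequate baseline or no post-baseline assessment. It censors at first dose unless the participant dies "on or before day 98) in which case the death will be considered an event". The same sentence stands in SAP 6.2.7 for PFS, where Table 2 footnote a supports it: "98 days after date of first dose the death is an event on the death date".

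The TTP tables differ from this bullet. Table 4 row 3 takes a death within 98 days of the last adequate assessment, or within 98 days of first dose, and censors it on the date of death. Table 4 row 1 censors every inadequate baseline at first dose, without the exception that Table 2 footnote a provides for PFS. Table 5 has a censoring reason for death, "No event and Death recorded in any disposition page or Notice of Death". The PFS list in Table 3 has none and closes with "No event and none of the conditions in the prior hierarchy are met". The planned TTP summary reads: "Frequency (number and percentage) of participants with PD and each censoring reasons will be presented".

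Protocol 9.4.1 has a clause for the same subgroup under each endpoint. For TTP, if the participant "dies within 12 weeks of the start date, in which case, the patient who be censored on date of death". For PFS, if the participant "dies within 12 weeks of the start date, in which case, death will be an event on date of death".

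**The concern.** TTP and PFS differ only in how they treat death without progression. A rule that makes some of those deaths TTP events turns TTP into PFS for one subgroup, while other deaths without progression stay censored. Two programmers who each follow SAP 6.2.8 faithfully could build different TTP datasets, for both the ICR and the investigator analyses. A death coded as an event would also have no row of its own in the planned table, which lists PD and censoring reasons only.

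**Working it through.** **1. The plan's own figure.** The gap limit is 12 weeks plus 2 weeks: (12 + 2) × 7 = 98 days, which agrees with the SAP. The protocol clause uses 12 × 7 = 84 days. A death on days 85 to 98 falls outside that clause, but nothing in the protocol makes it a TTP event. The difference in window therefore does not explain the conflict.

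**2. The TTP passages side by side, for an early death without PD in this subgroup.**

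| Place | Treatment of the death |
|---|---|
| SAP 6.2.8, bullet 3 | Event |
| SAP 6.2.8, Table 4 row 3 | Censored at date of death |
| SAP 6.2.8, Table 4 row 1 (inadequate baseline only) | Censored at first dose |
| SAP 6.2.8, Table 5 reason 7 | A censoring reason |
| Protocol 9.4.1, TTP | Censored at date of death |
| SAP 3.2.8 definition and 6.2.8 formula | Death is not included as an event |
| SAP 2.1 estimand | Follows to progression, "without regard to discontinuation from treatment unless participant dies" |
| SAP 2.1.2 TTP estimand | Death not mentioned |

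Only the bullet makes the death an event. The explicit censoring is in Tables 4 and 5 and in the protocol.

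**3. One participant.** Assume death on study day 60. TTP in months = (end date − start date + 1)/30.4375.

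- Adequate baseline, no later scan: the bullet gives an event at 60/30.4375 = 1.97 months. Table 4 row 3 and the protocol give censoring at 1.97 months. These are two codings.
- Inadequate baseline: the same two, plus Table 4 row 1, which censors at 1/30.4375 = 0.03 months. These are three codings.

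**4. Study level.** Let k of 70 participants die this way before any PD, with nobody else leaving the risk set first (assumptions). Coded as events, the deaths contribute (69/70) × (68/69) × … = (70 − k)/70 to the Kaplan-Meier estimate. Coded as censored at death, they contribute 1. The later risk sets are identical, so every later estimate is multiplied by (70 − k)/70. Starting from an assumed 12-month rate of 50%:

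| k | Factor | 12-month rate |
|---|---|---|
| 1 | 69/70 = 0.9857 | 49.3% |
| 2 | 68/70 = 0.9714 | 48.6% |
| 3 | 67/70 = 0.9571 | 47.9% |

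The approximate 95% half-width at n = 70 is 1.96 × √(0.5 × 0.5/70) = 0.117, or about 12 points.

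**5. Sensitivity.** The documents give neither a TTP median nor an early-death rate. Assume exponential TTP with median 8 months, follow-up of the others to 18 months, and deaths spread over the first 98 days. With k = 2, the 12-month rate is 34.3% with deaths as events and 35.5% with deaths censored at death; the median is 7.5 and 8.2 months. With k = 7, the rates are 31.4% and 35.5%, and the medians 6.6 and 8.4 months. Over assumed medians of 5.5, 8 and 12 months and k of 2, 4 and 7, the estimated median moves by about 0.5 to 2.1 months. The upper end needs 7 of 70 participants, or 10%, to die this way.

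**The case against.** The strongest defence is that protocol section 9 and SAP section 2 both allow the SAP to modify the protocol, and require an amendment only for major changes to the primary endpoint. A departure from protocol 9.4.1 on a secondary endpoint is therefore not an error in itself. That stands. It does not rescue the bullet, because Tables 4 and 5 of the same SAP section contradict it. An intended change would have been carried into them.

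The practical effect is also limited. A death coded as an event would still enter the overall event and censoring rates and the participant listing, and lacks only its own row. All deaths are tabulated and listed under SAP 6.6.2. A reader might infer from the order of reasons in Table 5 that these deaths go unreported. The hierarchy is a stated labelling rule for the TTP table, so that does not follow.

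Two further readings go too far:

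- A reader might infer that every other TTP passage expressly censors these deaths. The definition only leaves death out as an event, the SAP 2.1 estimand stops at it, and the SAP 2.1.2 estimand is silent.
- A reader might infer that bullet 3 is the only PFS wording left behind. All four TTP bullets repeat the PFS text. Bullet 4 covers only participants who are alive, so the bullets have no rule for a death without PD after adequate scans; only Table 4 row 3 supplies one. As the text reads, Table 4 also carries a marker b with no matching footnote.

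**Conclusion.** The third bullet of SAP 6.2.8 is wrong as written. It states a PFS rule for TTP, and it cannot be programmed together with Table 4 row 3 of the same section. This rests on the text and needs no assumption.

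It would be tempting to say that any such participant has three possible results. That holds only with an inadequate baseline; otherwise there are two. Nor do the documents support reading this as a threat to the study's conclusion. TTP is a secondary endpoint reported descriptively, and the only decision rule concerns the ORR, which this bullet does not touch.

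The size depends on an assumed number of early deaths. With 1 to 3 of 70 before any PD, a 50% 12-month rate falls by 0.7 to 2.1 points, well inside a half-width of about 12 points. Larger counts would move the median more, but the documents give no reason to expect them. The reason to act is that a stated rule would miscode data and the correction is simple.

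**What to change.** Make three text changes in SAP 6.2.8:

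1. In the third bullet, replace the clause that makes the early death an event with one that censors TTP at the date of death.
2. Add a footnote to Table 4 row 1: a participant with an inadequate baseline who dies no later than 98 days after first dose has TTP censored at the date of death. Rows 1 and 3 then agree.
3. Clear the remaining PFS carry-over. In the fourth bullet, add that a death without PD within 98 days of the last adequate assessment is censored at the date of death, as in Table 4 row 3. Correct the unmatched footnote marker b in Table 4.

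The PFS text in SAP 6.2.7 needs no change on this point. The cost is a few lines of SAP text, with no new data, no extra analysis and no change to the sample size.
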